4.1.3 Method of assigning patients to treatment groups

Once patients have completed screening, have met all the inclusion criteria and none of the exclusion criteria, a pre-treatment call will be made using the IRT system.

The Day 1 pre-treatment call will depend on the trial site procedure. The process for treatment assignment will be different depending on the country and respective trial medication shipping timelines. In countries where trial medication needs to be sent to sites in advance due to long shipping timelines (e.g., cross border shipments), trial medication will be provided to the sites in advance, and patients will be assigned treatment on Day 1. For countries where trial medication can be provided on short notice (short shipping times) a pre-treatment call will be made as described below and trial medication will be shipped. The pre-treatment call might be made 15 days prior to the planned first administration of trial medication.

At the beginning of Week 14, patients with at least a PASI50 response will be randomized to one of two sequences (1:1) to either switching or non-switching arm. At Week 14, the randomization will be stratified by the level of their Week 14 response (\geq PASI50 to < PASI75 or \geq PASI75). Access to the randomization code will be controlled and documented. The block sizes of the randomization will be documented in the clinical trial report (CTR).

Randomization will be performed by the IRT. Patients will be randomized sequentially (the lowest sequentially available randomization number).

Each syringe of trial medication will be labelled with the trial code and a unique medication identification number. The IRT system will be used for the randomization, allocation and supply of trial medication throughout the trial. The IRT will assign each patient a unique medication number. Details on the IRT system will be provided in the ISF.

Page 33 of 105

Proprietary confidential information © 2019 Boehringer Ingelheim International GmbH or one or more of its affiliated companies

4.1.4 Drug assignment and administration of doses for each patient

The trial design is described in Section 3.1.

Prefilled syringes will be used for the injections (see Section 4.1.1). Injections will be administered subcutaneously to the front of the thighs or abdomen/belly, at least 2 inches (about 5 centimeters) away from the navel. Rotate injection sites and do not give injections into areas where the skin is tender, bruised, red or hard.

After the first injection (Visit 2) and at randomization (Visit 9), the patient will remain at the clinical site for at least 1 hour for observation of any AEs.

Dose modification is not permitted during this trial. If a patient misses a dose of trial medication, then the dose should be administered as soon as possible. The 2-week regimen for trial medication administration should resume from the time the dose is administered. As soon as possible, the dosing should return to the original schedule and refer back to baseline. A minimum interval of 1 week between 2 successive injections should be adhered to.

In the event of an anaphylactic or other serious allergic reaction, the administration of trial medication will be discontinued immediately, the patient will be discontinued from the trial and appropriate therapy will be initiated.

4.1.5 Blinding and procedures for unblinding

4.1.5.1 Blinding

The trial is carried out in a double-blind fashion. Third-party blinding will be used to administer trial medication.

Access to the randomization code will be controlled and documented. All persons directly involved in the conduct of the trial will have no access to the treatment allocation prior to final database lock (see Section 4.1.5.2).

The randomization code will be kept secret by IRT up to database lock.

It is planned to conduct the trial using pre-filled syringes of $0.8 \text{ mL Humira}^{\otimes}$ (40 mg) as the reference product throughout.

However, if this 0.8 mL pre-filled Humira[®] syringe is not available for complete trial supply, the trial conduct may have to be continued using the 0.4 mL pre-filled Humira[®] syringe as the reference product. Taking into account that the 0.8 mL BI 695501 and the 0.4 mL Humira[®] presentations might differ, the blinding of treatments will be maintained by using a third-party blinding procedure. This means that the trial drug will be administered to the patients by persons who are independent of the other clinical trial procedures and not involved in other aspects of the trial (see Appendix 10.3 for details on third party blinding procedure). The secondary packaging (carton containing syringes) will be the same design for both BI 695501 and Humira[®]. The label text on secondary packaging (carton containing syringes) will be identical for both the products. However, the use-by date (expiry date) will be open.

Page 34 of 105

Proprietary confidential information © 2019 Boehringer Ingelheim International GmbH or one or more of its affiliated companies

4.1.5.2 Unblinding and breaking the code

Emergency unblinding will be available to the investigator / pharmacist / investigational drug storage manager via IRT. It must only be used in an emergency situation when the identity of the trial drug must be known to the investigator in order to provide appropriate medical treatment or otherwise assure safety of trial participants. The reason for unblinding must be documented in the source documents and/or appropriate eCRF page along with the date and the initials of the person who broke the code.

Due to the requirements to report Suspected Unexpected Serious Adverse Reactions (SUSARs), it may be necessary for a representative from BI's Pharmacovigilance group to access the randomisation code for individual patients during trial conduct. The access to the code will only be given to authorised Pharmacovigilance representatives and not be shared further.

4.1.6 Packaging, labelling, and re-supply

The investigational products will be provided by BI or a designated CRO. They will be packaged and labelled in accordance with the principles of Good Manufacturing Practice (GMP). Re-supply to the sites will be managed via an IRT system, which will also monitor expiry dates of supplies available at the sites.

For details of packaging and the description of the label, refer to the ISF.

4.1.7 Storage conditions

All trial medications must be kept in a secure place under appropriate storage conditions and handled according to GMP and GCP. Detailed storage conditions will be described on the trial medication labels.

If the storage conditions are found to be outside the specified range, the Clinical Research Associate (CRA) (as provided in the list of contacts in the ISF) must be contacted immediately.

4.1.8 Drug accountability

The designated person at each site will receive the investigational drugs delivered by the sponsor when the following requirements are fulfilled:

- Approval of the trial protocol by the Institutional Review Board (IRB)/Independent Ethics Committee (IEC);
- Availability of a signed and dated clinical trial contract between the sponsor and the head of the investigational site;
- Approval/notification of the regulatory authority, e.g., competent authority (CA);
- Availability of the curriculum vitae of the principal Investigator;
- Availability of a signed and dated CTP;
- Availability of the proof of a medical license for the principal Investigator; and
- Availability of Form 1572 (for US).

Page 35 of 105

Proprietary confidential information © 2019 Boehringer Ingelheim International GmbH or one or more of its affiliated companies

The designated person must maintain records of the investigational product's delivery to the trial site, the inventory at the site, the administration to each patient, and disposal of unused products. Unused trial medication will be destroyed in accordance with local requirements and the records will be maintained.

These records will include dates, quantities, batch / serial numbers, expiry ('use by') dates, and the unique code numbers assigned to the investigational product and trial patients. The designated person will maintain records that document adequately that the patients were provided the doses specified by the CTP and reconcile all investigational products received from the sponsor. At the time of disposal of unused products, the designated unblinded person must verify that all unused or partially used drug supplies have been returned by the clinical trial patient and that no remaining supplies are in the Investigator's possession.

4.2 OTHER TREATMENTS, EMERGENCY PROCEDURES, RESTRICTIONS

4.2.1 Other treatments and emergency procedures

There are no specific rescue drugs foreseen for the treatment of AEs. There are no special emergency procedures to be followed.

In case of AEs in need of treatment, the Investigator can authorise an appropriate therapy. In those cases, patients will be treated as necessary and, if required, kept under supervision at the trial site or transferred to a hospital until all medical evaluation results have returned to an acceptable level.

The Investigator must provide follow-up medical care for all patients who are prematurely withdrawn from the trial or must refer them for appropriate ongoing care according to local guidelines and daily practice, respectively.

4.2.2 Restrictions

4.2.2.1 Restrictions regarding concomitant treatment

Restrictions on prior and concomitant medications during the course of the trial are described in Table 4.2.2.1: 1.

Patients must be instructed not to take any new medications or to change the dose regimen of any existing medication (including over-the-counter products, herbal medications and complementary therapies) without first consulting with the Investigator. All changes must be noted in the concomitant medication section of the eCRF.

Other medication that is considered necessary for the patient's safety (e.g., as a result of an AE) may be given at the Investigator's discretion. Investigators are encouraged to discuss the introduction of any of the medications listed in Table 4.2.2.1: 1 with the CRO Medical Monitor.

Any concomitant medications will be recorded in the appropriate sections of the eCRF.

16011431-03 Clinical Trial Protocol Page 36 of 105
Proprietary confidential information © 2019 Boehringer Ingelheim International GmbH or one or more of its affiliated companies

Table 4.2.2.1: 1 Prior and concomitant treatments

Treatment	Restriction
Biologic agents (e.g., TNF antagonists, anti-IL12/23 and anti-IL17)	Previous or concomitant treatment with any biologic therapy for auto- immune diseases is not permitted. Concomitant medication with either anakinra or abatacept is not recommended.
Cyclophosphamide	Cyclophosphamide will not be permitted within 6 months prior to Visit 2/Day 1 and for the duration of the trial.
Topical steroids	Topical steroid treatment applied on psoriatic lesions/scalp/nails will not be permitted within 2 weeks prior to Visit 2/Day 1 and for the duration of the trial. Occlusive topical corticosteroids in any location will not be permitted within 2 weeks prior to Visit 2/Day 1 and for the duration of the trial. Topical corticosteroids of low potency (WHO group VI/VII) are permitted
	during the trial except within 24 hours before trial visits.
Other topical treatments	Other topical treatment applied on psoriatic lesions/scalp/nails that is likely to impact signs and symptoms of psoriasis (e.g., vitamin D analogues, pimecrolimus, retinoids, salicyl vaseline, salicylic acid, lactic acid, tacrolimus, tar, urea, hydroxy or fruit acids will not be permitted within 2 weeks of Visit 2/Day 1 and for the duration of the trial. However, use of emollients (moisturizing treatments) will be permitted during the trial duration except within the 24-hour period immediately prior to each clinic visit.
UVB or UVA or PUVA treatment	Treatment with UVB or UVA (without psoralen) will not be permitted within 2 weeks prior to Visit 2/Day 1 and for the duration of the trial. PUVA treatment will not be permitted within 4 weeks prior to randomization.
Traditional synthetic agents	Systemic treatment with traditional synthetic agents (e.g., methotrexate, sulphasalazine, azathioprine, retinoids, fumarates) will not be permitted within 4 weeks prior to Visit 2/Day 1 and for the duration of the trial.
Nutraceutical treatments	Nutraceuticals intended for the treatment of psoriasis will not be permitted within 4 weeks prior to Visit 2/Day 1 and for the duration of this trial.
Other systemic or locally acting medications	Treatment with any other systemic or locally acting medications which might counter or influence the objective of the trial (e.g., NSAID, antihistamine), or medications known to provoke/aggravate psoriasis (e.g., lithium, beta-blockers or antimalarial drugs), will only be permitted if the doses of such agents are stable within 4 weeks prior to Visit 2/Day 1 and are planned to remain so for the duration of this trial.
Live/attenuated vaccine	Not permitted within 12 weeks prior to the Screening Visit, for the duration of the trial and up to 3 months after the last dose of trial drug.
Any drug/therapy that has not received regulatory approval for any indication	Not permitted within 12 weeks or a minimum of five half-lives, whichever is longer, prior to Visit 2/Day 1.
IV Gamma Globulin	Not permitted within 6 months of the Screening Visit.
Intravenous, intramuscular, intra- articular or parenteral corticosteroids	Not permitted within 6 weeks prior to Visit 2/Day 1 or throughout the trial.
Oral corticosteroids	Not permitted within 4 weeks prior to Visit 2/Day 1 or throughout the trial.
Prosorba® Column	Not permitted within 6 months of the Screening Visit.
Leflunomide	Not permitted. Must be withdrawn at least 8 weeks prior to Visit 2/Day 1.

Clinical Trial Protocol

Page 37 of 105 Proprietary confidential information © 2019 Boehringer Ingelheim International GmbH or one or more of its affiliated companies

Abbreviations: IL=interleukin; IV=intravenous; NSAID=nonsteroidal anti-inflammatory drugs; PUVA= psoralen with ultraviolet light; TNF=tumor necrosis factor; UVA=ultraviolet A light; UVB=ultraviolet B light; WHO=World Health Organization.

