3.3 SELECTION OF TRIAL POPULATION

Approximately 240 patients will be randomized in approximately 80 clinical sites across approximately 12 countries.

A log of all patients enrolled into the trial (i.e. who have signed informed consent) will be maintained in the ISF at the investigational site irrespective of whether they have been treated with investigational drug or not.

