3.3.3 Exclusion criteria

1. Active ongoing inflammatory diseases other than psoriasis that might confound trial evaluations according to Investigator's judgment.

- 2. Prior exposure to any biologic therapies for any auto-immune diseases (eg: RA, Psoriasis, Crohns Disease, etc).
- 3. Patients with a significant disease other than psoriasis and/or a significant uncontrolled disease (such as, but not limited to, nervous system, renal, hepatic, endocrine, hematological, autoimmune or gastrointestinal disorders). A significant disease is defined as a disease which, in the opinion of the Investigator, may (i) put the patient at risk because of participation in the trial, or (ii) influence the results of the trial, or (iii) cause concern regarding the patient's ability to participate in the trial.
- 4. Major surgery (major according to the Investigator's assessment) performed within 12 weeks before enrollment or planned within 6 months after screening, e.g., total hip replacement.
- 5. Any documented active or suspected malignancy or history of malignancy within 5 years prior to screening, except appropriately treated (in the opinion of the Investigator) basal cell carcinoma of the skin or in situ carcinoma of uterine cervix.
- 6. Patients who must or wish to continue the intake of restricted medications (see Section 4.2.2.1) or any drug considered likely to interfere with the safe conduct of the trial.
- 7. Currently enrolled in another investigational device or drug trial, or less than 30 days (or less than 5 half-lives, whichever is longer) since ending another investigational device or drug trial(s), or receiving other investigational treatment(s).
- 8. Chronic alcohol or drug abuse or any condition that, in the Investigator's opinion, makes the patient an unreliable trial subject or unlikely to complete the trial.
- 9. Women who are pregnant, nursing, or who plan to become pregnant during the course of this trial or within the period at least 6 months following completion or discontinuation from the trial medication.
- 10. Forms of psoriasis (e.g., pustular, erythrodermic and guttate) other than chronic plaque psoriasis. Drug-induced psoriasis (i.e., new onset or current exacerbation from e.g., beta blockers or lithium).
- 11. Primary or secondary immunodeficiency (history of, or currently active), including known history of HIV infection or a positive HIV test at screening (per the Investigator discretion and where mandated by local authorities).

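### The PUVA restriction in Table 4.2.2.1: 1 is tied to randomization and has no on-trial ban, so no listed restriction bars PUVA after Week 14

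*Protocol*

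**What the plan says.** Table 4.2.2.1: 1 in Protocol Section 4.2.2.1 has one row for UVB, UVA and PUVA, with two sentences. For light without psoralen it says "Treatment with UVB or UVA (without psoralen) will not be permitted within 2 weeks prior to Visit 2/Day 1" and extends the ban over the whole trial. For PUVA it says only "PUVA treatment will not be permitted within 4 weeks prior to randomization".

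The neighbouring rows follow the first pattern. Traditional synthetic agents are barred "within 4 weeks prior to Visit 2/Day 1 and for the duration of the trial". Steroids applied to lesions, other active topicals and nutraceuticals for psoriasis likewise have a window before Visit 2/Day 1 and a whole-trial ban (low-potency topical steroids are a stated exception).

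Sections 3.1, 4.1.3 and 7.7 place randomization at Week 14 (Visit 9, Day 92 in the Flow Chart), after the Humira run-in.

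Three rules depend on the table or on what counts as a violation:

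- Exclusion criterion 6 covers "Patients who must or wish to continue the intake of restricted medications (see Section 4.2.2.1").
- Section 7.6.2 makes a patient a non-responder after a severe violation involving a therapy that may affect efficacy, and cites the table.
- The Per Protocol Set definition in Section 7.3 removes protocol violations relevant to efficacy.

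**The concern.** PUVA is an active psoriasis treatment. Section 1.1 describes ultraviolet light, with or without psoralen, as effective in mild to moderate disease, and inclusion criterion 4 admits candidates for phototherapy. Patients between PASI50 and PASI75 at Week 14 are randomized and kept on treatment, so some have residual disease that might prompt added therapy.

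The words in brackets in the UVB/UVA sentence take PUVA out of that sentence, so its whole-trial ban does not carry over. At stake is consistent scoring at Week 32. A patient who adds UVB breaches a listed restriction and can be set to non-responder or removed from the Per Protocol Set. A patient who adds PUVA and stays on study drug may breach nothing, and could count as a PASI75 or sPGA responder.

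**Working it through.** The check is a comparison of texts plus calendar arithmetic. The plan gives no figure to reproduce.

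**Inputs (Flow Chart).** Baseline is Day 1, Week 10 is Day 64, Week 14 is Day 92 and Week 32 is Day 218. The PUVA window is 4 weeks, or 28 days.

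**Literal reading: randomization means Week 14.**
- Barred window: 92 − 28 = 64, so Day 64 to Day 92. This lies inside the run-in.
- There is no washout before the baseline PASI on Day 1.
- Unrestricted run-in time: (64 − 1)/7 = 9 weeks.
- Unrestricted time from randomization to Week 32: (218 − 92)/7 = 18 weeks.
- Total up to Week 32: 9 + 18 = 27 weeks.

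**Slip reading: randomization means Visit 2/Day 1.**
- The barred window is the 4 weeks before Day 1, so the washout is sound.
- Unrestricted time up to Week 32: (218 − 1)/7 = 31 weeks.

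**Which reading is likelier.** The protocol uses the term loosely elsewhere. Section 3.3 says "Approximately 240 patients will be randomized in approximately 80 clinical sites", whereas the synopsis gives about 240 as the number entered into the run-in and about 96 per arm as the number randomized. The synopsis counts the 6-month disease history back from randomization, where inclusion criterion 1 counts from first dose. Section 3.3.4 says that ineligible patients are not randomized and are screen failures. A slip for Day 1 is therefore probable. The 18 weeks after Week 14 are open on both readings.

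**Does other text close the gap after Week 14?**
- Section 4.2.2.1 tells patients not to start new medication "without first consulting with the Investigator". That is a consultation step, not a ban.
- The stable-dose row begins "Treatment with any other systemic or locally acting medications which might counter or influence the objective of the trial". It covers treatments other than those listed, and PUVA has its own row.
- Section 4.2.2.2 bars tanning beds and moisturizers or emollients containing retinoids only.
- Section 3.3.4.1 allows withdrawal for severe worsening. Those who discontinue treatment before the endpoint are already non-responders under Section 7.6.2, so the gap concerns only patients who stay on treatment.

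**Illustrative size.** The number of PUVA users is not given. Assume 0 to 3 patients in an arm of 96 whose response was due to PUVA:
- Shift in that arm's rate: 0 to 3/96 = 3.1 percentage points. With balanced use the arm difference does not move.
- 95% Wald half-width for the difference, 96 per arm, common response rate p: 1.96 × √(2p(1 − p)/96).

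| Assumed p | Half-width (percentage points) |
|---|---|
| 0.7 | 13.0 |
| 0.8 | 11.3 |
| 0.9 | 8.5 |

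Even the one-sided case of 3 patients is well inside the interval's half-width.

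**The case against.** Four things can be said on the other side.

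First, a reader might infer that no on-trial PUVA breaches any restriction. The text does not support that: read literally, the sentence bars PUVA from Day 64 to Day 92, which is on trial. This objection stands, and the point is limited to the period after randomization, where both readings agree.

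Second, a reader might infer that exclusion criterion 6 cannot reach PUVA. That also goes too far. PUVA has a row in the table of restrictions to which the criterion refers, so a patient who wishes to continue it is plausibly ineligible, and an eligibility violation can count against the Per Protocol Set. This stands too. What remains is PUVA newly started on trial.

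Third, psoralen begun on trial could be argued to fall under the stable-dose row, and investigators are encouraged to discuss listed medications with the CRO medical monitor. This is partial cover at best. The row is for other medications, and a discussion is not a prohibition.

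Fourth, Section 7.6.2 and the Per Protocol Set rule rest on judgement, with detail left to the TSAP, which is not shown. So one cannot say that they would fail to catch PUVA, only that they may. It remains awkward, though, to class as a violation something that no listed restriction forbids.

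Nor is PUVA the only entry with just a pre-trial window. The row for unapproved therapies reads "Not permitted within 12 weeks or a minimum of five half-lives, whichever is longer, prior to Visit 2/Day 1", and IV gamma globulin and the Prosorba column are treated alike. The comparison holds for the named conventional psoriasis therapies only.

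**Conclusion.** The sentence is wrong as written, and the point is minor. Its anchor is either an error or leaves baseline without a washout, and on both readings no listed restriction bars PUVA in the 18 weeks between randomization and the Week 32 efficacy assessment. PUVA newly started by a patient who stays on treatment may therefore escape the Section 7.6.2 non-responder rule and Per Protocol Set exclusion, subject to the TSAP.

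The effect is limited to PASI75 and sPGA at Week 32, which Section 2.1.1 treats descriptively. The size in percentage points rests on an assumed number of users and assumed response rates. The trial is double-blind, and nothing in the protocol suggests that use would differ between arms.

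A reader might infer a threat to the primary analysis. The protocol does not support that: the endpoints are adalimumab concentrations, and Section 7.3 considers restricted medications there only where an impact on PK is suspected. The primary PK comparison is not materially affected.

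**What to change.** In the UVB/UVA/PUVA row of Table 4.2.2.1: 1, change the end of the PUVA sentence so that PUVA is not permitted "within 4 weeks prior to Visit 2/Day 1 and for the duration of the trial". This matches the row for traditional synthetic agents. It corrects the anchor and adds the missing ban in one step. Exclusion criterion 6, Section 7.6.2 and the Per Protocol Set rule then apply to PUVA as they do to UVB and UVA.

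The cost is one table row. No other section, procedure or analysis needs to change.
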